### **Statistical Approach & Expected Outcomes**

**General Data Analytic Approach.** We will conduct repeated measures analyses (i.e., across time) using generalized linear mixed modeling (GLMM; Proc MIXED, Proc GLIMMIX, and Proc MCMC; SAS 9.4). Continuous and count data will be analyzed using linear and Poisson regression, respectively (Proc GENMOD; SAS v. 9.4). Evaluation of distributional assumptions will use residual plots and, where possible, formal statistical tests. Depending upon statistical technique, we will address violations of assumptions using transformations, robust estimators, stratification, and/or scaling coefficients. For instance, given the characteristically skewed nature of the TNE distribution the analytic plan and power discuss this variable in its log form. Analyses of data with missing values will utilize multiple imputation for cross-sectional analyses (Proc MI and Proc MIANALYZE; SAS v.9.4) [126], while analyses of repeated measures will rely on GLMM to maximize use of existing data. For analyses that require assessment for differential patterns of missing data, we will use Little's Test of MCAR for continuous outcomes and the Park and Lee's approach for discrete outcomes [127, 128]. We will use pattern-mixture modeling methods to address non-ignorable missing data patterns [129]. We will use sensitivity analyses to evaluate the robustness of findings to missing data assumptions. Finally, the False Discovery Rate approach will be used to correct for multiple testing [130].

***Aim 1: To characterize the effects of switching to VLNCCs plus ECIG-Hi or ECIG-Lo nicotine doses on abuse liability among daily and intermittent smokers.*** Our primary measures of abuse liability will be CPD (product use) and nicotine equivalent (TNE) levels (nicotine compensation). We hypothesize that compared with the VLNC+ECIG-Lo phase, smokers will show decreased CPD and TNE levels during the VLNC+ECIG-Hi phase. To address these hypotheses, we will use GLMM to evaluate the effects of ECIG dose on measures of nicotine abuse liability, including cigarettes per day and TNE levels.

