**Aim 3 (exploratory): To explore the effects of switching from usual-brand cigarettes to VLNCCs, and from VLNCCs to VLNCC+ECIGs on measures of abuse liability.** On an exploratory basis, we will examine potential changes in the abuse liability measures from Aims 1 & 2 between the UB cigarette and VLNCC only phases, and between those phases and the dual-use phases (VLNC+ECIG-Lo and VLNC+ECIG-Hi). We will use GLMM to evaluate the study phase (UB cigarettes, VLNCCs, VLNC+ECIG-Lo, VLNC+ECIG-Hi) and the measures of abuse liability from Aims 1 & 2 to characterize the impact of transitioning between study nicotine products over time.

**Aim 4 (exploratory): To characterize the effects of dual use of VLNCC and JUUL ECIGs on abuse liability.** On an exploratory basis, we will examine the differences in measures of abuse liability between the two phases of dual-use (VLNC+JUUL-Lo vs. VLNC+JUUL-Hi) among participants assigned to the JUUL ECIG arm. We will use GLMM to evaluate the effects of JUUL dose on measures of nicotine abuse liability, including patterns of product use (UB and VLNCC CPD, ECIG puff count), nicotine compensation (TNE, MA, expired CO), product liking (IAT, Product Evaluation Scales, perceived harm, PHR), RRE (Purchase Task indices).

**Power analysis.** Sample size determination for the current proposal focuses on our primary outcomes for the Aim 1 hypothesis. Effect size estimates are based on our U54 data using the usual brand baseline and 0.03 mg VLNCC conditions to estimate CPD and TNE from those two conditions, respectively [9]. There is no extant data to draw upon for VLNCC+ECIG-Hi or ECIG-Lo conditions for either DS or ITS. Hence, we attempted to estimate the means and standard deviations for CPD and TNE for these two conditions using data from the U54, using

**Table 1.** Anticipated effects for DS and ITS, by Phase and E-Cig group.

Primary Outcome	Phase 1: Usual Brand	Phase 2: VLNC Only	Phase 3: VLNC + ECIGs-HI	Phase 4: VLNC + ECIGs-LO
DS				
CPD	19.62 (10.18)	14.19 (10.09) a	12.80 (10.00) b	12.80 (10.00) b
TNE	63.01 (55.87)	33.54 (34.84)	59.50 (53.88)	33.08 (31.27)
log(TNE)	3.89 (0.99)	2.69 (1.65) a	3.60 (1.28) c	2.72 (1.62) b
ITS				
CPD	3.42 (3.44)	2.47 (3.44) a	1.57 (3.44) c	1.57 (3.44) c
TNE	32.5 (17.53)	10 (9.36)	28.37 (22.24)	15.88 (11.16)

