log(TNE)	3.31 (0.67)	1.74 (1.49) a	3.07 (0.80) c	2.31 (1.29) c

Primary outcomes are for nicotine compensation (TNE) and CPD. **a**-Significant change between Phase 1 & 2 expected; **b**-No significant change from Phase 2 to 3 expected; **c**-Significant change from Phase 2 to 3 expected.

the entire sample for DS, and for ITS, limiting the sample to participants in the lowest centile of baseline CPD (<7.3 cigarettes per day). These presumptive means and standard deviations are provided in **Table 1**. While these estimates are not exact they provide a reasonable estimate of the behavior of two groups that vary significantly in their CPD

**Table 2.** Power Estimates.

Contrast	Anticipated Effect Sizes		Power		Minimum Detectable Effect Size	
	DS	CPD (R.R.*)	Log(TNE) ( $d_z^{**}$ )	CPD	Log(TNE)	CPD R.R. (Power)
Within Group						
Brand v. VLNC	0.72	-0.78	$\geq 99\%$	$\geq 99\%$	0.89 (83%)	-0.39 (82%)
VLNC v. VLNC-ECIG-HI	0.90	0.56	61.4% x	$\geq 99\%$	0.88 (82%)	0.35 (81%)
VLNC v. VLNC-ECIG-LO	0.90	0.02	61.4% x	5% x	0.88 (82%)	0.36 (82%)
VLNC-ECIG-HI v. VLNC-ECIG-LO	1.00	-0.55	5% x	$\geq 99\%$	1.13 (81%)	-0.35 (80%)
ITS						
Brand v. VLNC	0.72	-1.15	93.9%	$\geq 99\%$	0.76 (82%)	-0.35 (81%)
VLNC v. VLNC-ECIG-HI	0.64	0.96	98.7%	$\geq 99\%$	0.73 (80%)	0.35 (83%)
VLNC v. VLNC-ECIG-LO	0.64	0.37	98.7%	85.7%	0.73 (80%)	0.35 (80%)
VLNC-ECIG-HI v. VLNC-ECIG-LO	1.00	-0.63	5% x	$\geq 99\%$	1.40 (82%)	-0.35 (82%)

\*Risk Ratio. \*\* Standardized effect size accounting for correlation. xNo change expected.

rate across visits ranged from 92%-100%), we based our power analysis on n = 67 DS and n = 67 ITS.

**Table 2** provides power estimates for respective contrasts. For within-group effects the overall posited correlation between adjacent phases was 0.4. Each power estimate was derived from K = 1000 Monte Carlo simulations. **Table 2** summarizes minimally detectable effects, given the anticipated sample size, alpha = 0.05, and the correlations due to repeated measures.

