**Table 2** also includes minimum detectable effects and corresponding power for each contrast. Minimum detectable effects for CPD (i.e., 80-83% Power) range for Risk Ratios indicating 11% to 40% relative changes for within-group contrasts. Absolute values for standardized effect sizes that constitute minimum detectable effects for log(TNE) (i.e., 80% Power) range from absolute values of  $d_z$  = 0.35 to 0.39 for within-group contrasts. While we do not anticipate significant changes in CPD from Phases 2 to Phase 3 or 4 among DS participants, the study will be powered to detect a risk ratio for CPD of 0.88 for VLNC vs. ECIG-HI or ECIG-LO, and a risk ratio of 1.13 for the difference in CPD between VLNC + ECIG-HI and VLNC + ECIG-LO. Similarly, among DS participants we do not anticipate a change in log(TNE) moving from VLNC to VLNC-ECIG-LO, however the sample will provide power to detect a standardized effect size of  $d_z \geq 0.36$ . Among ITS participants, we do not anticipate differences between VLNC + ECIG-HI and VLNC + ECIG-LO in CPD but the sample will provide power to detect a risk ratio of 1.40 if an effect does occur. Power estimates for the exploratory Aims 2, 3, and 4 analyses focuses on the GLMMs for self-report and volatility measures; TVEM approaches will have many more observations than either of these, however fitting the functional form of change over time, and therefore its final parameterization will be largely data-dependent. Assuming alpha = 0.05 and a correlation of r = 0.5 for repeated measures, a sample of n = 67 DS participants provides 80% power for the GLMM to detect a Cohen's f = 0.17. The Aim 4 hypotheses are considered exploratory and were not subject to power analyses, but we should have adequate statistical power to detect the hypothesized differences because it will use the same sample size, design, and outcome measures as Aims 1 & 2.

and variation in their behavior when exposed to conditions of relatively more (Usual Brand) vs. less (0.03 mg) nicotine availability. Power estimates are based on Monte Carlo simulation or calculations using G\*Power 3.0 [136]. We anticipate enrollment of up to 380 participants (including at least 80 ITS). Assuming 15% loss to attrition (in our U54 the completion

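### Table 2's CPD powers do not follow from Table 1's SDs, r = 0.4 and n = 67: for ECIG-Hi v ECIG-Lo they should be about 23% (DS) and 27% (ITS), not 81% and 82%

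*Combined protocol and SAP*

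**What the plan says.** All of this is in Section D of the combined protocol and SAP, under Statistical Approach & Expected Outcomes.

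- **Purpose of the power analysis:** "Sample size determination for the current proposal focuses on our primary outcomes for the Aim 1 hypothesis". Aim 1 has two primary outcomes, CPD and TNE, and predicts that "smokers will show decreased CPD and TNE levels during the VLNC+ECIG-Hi phase" relative to ECIG-Lo.
- **Inputs:** Table 1 gives assumed means and SDs by phase. In both dual-use phases CPD is 12.80 (SD 10.00) for DS and 1.57 (SD 3.44) for ITS. "For within-group effects the overall posited correlation between adjacent phases was 0.4", alpha is 0.05, and "we based our power analysis on n = 67 DS and n = 67 ITS".
- **Outputs:** Table 2 anticipates a CPD ratio of 1.00 for Hi v Lo in both groups. It gives minimum detectable ratios of 1.13 (81% power, DS) and 1.40 (82% power, ITS). The text repeats the DS claim as "a risk ratio of 1.13 for the difference in CPD between VLNC + ECIG-HI and VLNC + ECIG-LO" and says of ITS that "the sample will provide power to detect a risk ratio of 1.40 if an effect does occur". It summarises: "Minimum detectable effects for CPD (i.e., 80-83% Power) range for Risk Ratios indicating 11% to 40% relative changes for within-group contrasts".
- **Analysis:** "Continuous and count data will be analyzed using linear and Poisson regression, respectively". Aim 1 itself is assigned to a generalized linear mixed model. Robust estimators and scaling coefficients are listed as remedies if assumptions fail.

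**The concern.** An SD of 10 on a mean of 12.8 is large. With a correlation of 0.4, the SD of a within-person difference is about 11 cigarettes. A ratio of 1.13 is a difference of under 2 cigarettes, and 67 pairs could not be expected to show it with 81% power.

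Because Table 2 anticipates no Hi v Lo difference in CPD, the minimum detectable ratios are the plan's only statement of what CPD effect the trial could find. If they are too optimistic, a null CPD result could be misread as evidence against a 13% difference in DS or a 40% difference in ITS.

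**Working it through.** **Inputs.** Means and SDs from Table 1; r = 0.4, alpha = 0.05 and n = 67 per group from the power analysis. Sidedness is not stated; two-sided is assumed.

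**Formula.** SD of difference = sqrt(s1² + s2² − 2·r·s1·s2); dz = difference / SD of difference; power from the noncentral t with n − 1 degrees of freedom.

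**Step 1: reproduce the plan's log(TNE) effect sizes.** For DS Hi v Lo, SD of difference = sqrt(1.28² + 1.62² − 0.8 × 1.28 × 1.62) = 1.614, so dz = (2.72 − 3.60)/1.614 = −0.545 (printed −0.55). All eight agree with Table 2 within rounding:

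- DS: −0.775, 0.557, 0.017, −0.545 (printed −0.78, 0.56, 0.02, −0.55)
- ITS: −1.148, 0.963, 0.372, −0.625 (printed −1.15, 0.96, 0.37, −0.63)

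The log(TNE) column therefore uses Table 1's SDs with r = 0.4. Also, dz = 0.35 at n = 67 gives 80.6% power, in line with the printed detectable values.

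**Step 2: apply the same inputs to CPD, Hi v Lo.**

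- DS, ratio 1.13: difference = 0.13 × 12.80 = 1.664; SD of difference = 10 × sqrt(1.2) = 10.95; dz = 0.152; power 23.2% (printed 81%).
- ITS, ratio 1.40: difference = 0.40 × 1.57 = 0.628; SD of difference = 3.44 × sqrt(1.2) = 3.77; dz = 0.167; power 27.0% (printed 82%).

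**Step 3: all non-null CPD entries.** The last column is the correlation that would give the printed power at n = 67 with Table 1's SDs.

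| Group, contrast | Ratio | Printed | Recomputed | r needed |
|---|---|---|---|---|
| DS brand v VLNC, anticipated | 0.72 | ≥99% | 98% | – |
| DS brand v VLNC, detectable | 0.89 | 83% | 35% | 0.83 |
| DS VLNC v Hi or Lo, anticipated | 0.90 | 61.4% | 18% | 0.88 |
| DS VLNC v Hi or Lo, detectable | 0.88 | 82% | 24% | 0.89 |
| **DS Hi v Lo, detectable** | 1.13 | 81% | 23% | 0.89 |
| ITS brand v VLNC, anticipated | 0.72 | 93.9% | 53% | 0.80 |
| ITS brand v VLNC, detectable | 0.76 | 82% | 42% | 0.78 |
| ITS VLNC v Hi or Lo, anticipated | 0.64 | 98.7% | 49% | 0.87 |
| ITS VLNC v Hi or Lo, detectable | 0.73 | 80% | 30% | 0.84 |
| **ITS Hi v Lo, detectable** | 1.40 | 82% | 27% | 0.87 |

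Only the first row and the 5% entries at ratio 1.00 are consistent with the inputs.

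**Step 4: ratio detectable with 80% power.** At n = 67 this needs dz = 0.347. DS: 1 + 0.347 × 10.95/12.80 = 1.30. ITS: 1 + 0.347 × 3.77/1.57 = 1.83. A log-ratio calculation with constant coefficient of variation gives exp(2.80 × 0.1046) = 1.34 and exp(2.80 × 0.293) = 2.27. Keeping the printed ratios and powers would take about 351 DS and 300 ITS completers.

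**Step 5: sensitivity of the Hi v Lo result.**

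- Method: a delta-method log ratio with Table 1's SDs gives 23.4% (DS) and 25.4% (ITS). Over-dispersed count simulations with robust SEs give 24–25% and 28.5–30%.
- One-sided test: 34% and 39%.
- Ratio taken in the opposite direction: 19% and 16%.
- DS with r = 0.5, 0.6, 0.7, 0.8: 27%, 32%, 41%, 56%.
- Fewer ITS: 77% retention of 80 gives 61 completers and 25% power.
- More DS: if 220 enter the eGo arm (an assumption: 380 − 80 ITS − 80 JUUL), 77% to 85% retention leaves 169 to 187 completers and 50% to 54% power.

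**Step 6: a possible source.** If CPD variance equalled its mean and phases were independent, the SE of the log ratio would be sqrt((1/m1 + 1/m2)/67). Power would then be 83% for DS 0.89 (printed 83%), 59% for DS 0.90 (61.4%), 77% for DS 0.88 (82%) and 74% for DS 1.13 (81%). That is fairly close, but the plan states no CPD variance assumption, so this is inference. Table 1's CPD variances are 3.5 to 7.8 times the means (for example 11.83/3.42 and 100/12.8).

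**The case against.** The strongest reply is that Aim 1 names a mixed model. A Poisson model with a subject random intercept sized to Table 1's first-phase SD, at n = 67, gives powers not far below print: about 74% for DS 1.13, 59–61% for DS 0.90, 82–83% for DS 0.89 and 74% for ITS 1.40. It also rejects the null about 4–5% of the time. So Table 1's spread and n = 67 can coexist with roughly the printed powers.

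That is true, but such a model fixes the raw between-phase correlation. For Hi v Lo with equal means it is (variance − mean)/variance: (100 − 12.8)/100 = 0.87 for DS and (11.83 − 1.57)/11.83 = 0.87 for ITS. Across contrasts it is about 0.67 to 0.88. This is not the stated 0.4, and the plan gives no separate correlation or other scale for CPD. The reply identifies which input may be wrong; it does not reconcile the figures.

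Three narrower points stand in part:

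- True power need not be 23%. Smokers' CPD may correlate above 0.4 between phases, and the plan admits that its estimates are inexact. The finding is about what follows from the stated inputs.
- The result depends somewhat on the variance rule. With a constant coefficient of variation, ITS 0.72 and 0.64 rise to about 68% and 67%, and ITS 1.40 falls to about 21%. All remain well below print.
- A larger DS group would reduce the DS shortfall but not remove it at r = 0.4. With 169 completers, a correlation of about 0.7 would be needed to reach 79%.

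**Conclusion.** The concern holds. Table 1's SDs, r = 0.4 and n = 67 cannot all be true alongside Table 2's CPD powers. For the Hi v Lo contrast behind Aim 1, power at the claimed detectable ratios is about 23% (DS) and 27% (ITS), roughly a third of the printed values. The stated sensitivity to CPD changes of 11% to 40% is unsupported.

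This assumes a two-sided test, one CPD value per participant per phase, and 0.4 as the correlation between those values. The log(TNE) figures are unaffected. The discrepancy does not show that the trial is too small for its other primary outcome, and the cause of the error cannot be established from the documents. It should be fixed because it misstates what the trial can detect on a primary outcome.

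**What to change.** 1. Recompute the CPD power and minimum-detectable columns of Table 2, and the paragraph that repeats them, from Table 1's means and SDs with r = 0.4. Alternatively, state and justify a different CPD correlation and variance model and show that it yields the printed figures.
2. Use the analysable numbers now expected. Potential Problems & Alternative Strategies reports 77% retention, which leaves about 61 of 80 ITS. State the planned number of DS in the eGo arm.
3. Secondary: make the primary CPD model robust to over-dispersion by default (negative binomial, or Poisson with estimated dispersion or sandwich SEs). This matters if r really is near 0.4. For DS Hi v Lo, the SE of the log ratio would then be sqrt(1.2) × (10/12.8)/sqrt(67) = 0.1046, against a Poisson model-based 0.0483, and an uncorrected test would reject a true null about 36–37% of the time. If the correlation is as high as the random-intercept model implies, that problem largely disappears. The plan's existing remedies cover this only after a violation is found.

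The cost is a rerun of the simulation and edits to Table 2, one paragraph of the power analysis and one sentence of the general analytic approach. The stated CPD power will look much less favourable.

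### Aim 1 predicts lower CPD on ECIG-Hi than on ECIG-Lo, but Tables 1 and 2 plan for no CPD difference, and the detectable CPD ratios quoted beside them look optimistic

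*Combined protocol and SAP*

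**What the plan says.** Aim 1 is stated in Specific Aims and again in Statistical Approach & Expected Outcomes. On the outcomes: "Our primary measures of abuse liability will be CPD (product use) and nicotine equivalent (TNE) levels". On the direction: "We hypothesize that compared with the VLNC+ECIG-Lo phase, smokers will show decreased CPD and TNE levels during the VLNC+ECIG-Hi phase". Aims 2 to 4 are labelled exploratory, so this is the only confirmatory hypothesis.

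The Power analysis opens with "Sample size determination for the current proposal focuses on our primary outcomes for the Aim 1 hypothesis". Its tables then give, for ECIG-Hi against ECIG-Lo on CPD:

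| | Table 1 CPD, Hi (SD) | Table 1 CPD, Lo (SD) | Table 2 anticipated ratio | Table 2 power | Table 2 detectable ratio (power) |
|---|---|---|---|---|---|
| Daily smokers (DS) | 12.80 (10.00) | 12.80 (10.00) | 1.00 | 5%, flagged x | 1.13 (81%) |
| Intermittent smokers (ITS) | 1.57 (3.44) | 1.57 (3.44) | 1.00 | 5%, flagged x | 1.40 (82%) |

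The x flag is explained as "No change expected". For ITS the text repeats this in words: "we do not anticipate differences between VLNC + ECIG-HI and VLNC + ECIG-LO in CPD". There is no matching sentence for DS on Hi against Lo. The DS sentence about not anticipating a CPD change concerns the move from Phase 2 to Phases 3 and 4, so for DS the evidence is the table entries.

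The power figures use 67 DS and 67 ITS, alpha 0.05, and a correlation of 0.4 between adjacent phases.

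**The concern.** The plan hypothesises a CPD reduction and, in the tables said to serve that hypothesis, plans for none. CPD is one of two primary measures.

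What is at stake is how the result will be read. A non-significant Hi against Lo CPD contrast would be both what Table 2 anticipates and a failure to support Aim 1. A significant reduction would confirm Aim 1 and contradict Tables 1 and 2. Either account could be written after the data are seen. The study is meant to inform regulation of e-cigarette nicotine dose, so this should be settled beforehand.

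**Working it through.** **1. Is 1.00 the intended planning value, or damage to the table?** Table 2's CPD ratio is the second-named phase divided by the first-named. The other rows reproduce from Table 1:
- Usual brand v VLNC: DS 14.19/19.62 = 0.72; ITS 2.47/3.42 = 0.72 (stated 0.72 in both).
- VLNC v VLNC + ECIG: DS 12.80/14.19 = 0.90; ITS 1.57/2.47 = 0.64 (stated 0.90 and 0.64).
- Hi v Lo: DS 12.80/12.80 = 1.00; ITS 1.57/1.57 = 1.00 (stated 1.00 in both).

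So 1.00 is intended.

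**2. The stated 5%.** At a ratio of 1.00, the rejection probability of a two-sided 0.05 test is 0.05 at any n. In the hypothesised direction (Hi lower) it is about 0.025. A simulation of correlated Poisson counts (n = 67, r = 0.4, 4,000 runs) gave 5.0% in DS and 4.7% in ITS. The plan's figure is reproduced. The plan does not state whether the test is one- or two-sided; two-sided is assumed.

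**3. What the detectable ratios mean.** With the same convention the ratio is Lo/Hi. The hypothesised direction therefore needs Hi to lower CPD by 1 − 1/1.13 = 11.5% in DS, or 1 − 1/1.40 = 28.6% in ITS. The plan anticipates neither.

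**4. What variance those ratios rest on.**

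Poisson variance, Wald test on the log ratio, with m1 = Hi mean, m2 = Lo mean, n = 67:

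SE² = (1/m1 + 1/m2 − 2r/√(m1·m2))/n

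- DS, m1 = 12.80, m2 = 12.80 × 1.13 = 14.46, ln 1.13 = 0.122. With r = 0: SE = 0.0469, z = 2.61, power 74%. With r = 0.4: SE = 0.0363, z = 3.36, power 92%.
- ITS, m1 = 1.57, m2 = 1.57 × 1.40 = 2.198, ln 1.40 = 0.336. With r = 0: SE = 0.128, z = 2.64, power 75%. With r = 0.4: SE = 0.0993, z = 3.39, power 92%.

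These bracket the stated 81% and 82%. The anticipated DS contrast of VLNC v VLNC + ECIG behaves likewise: stated 61.4%; Poisson 59% (r = 0) to 81% (r = 0.4).

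Table 1's SDs, paired t-test, r = 0.4:

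dz = m1(RR − 1)/√(2·SD²·(1 − r))

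- DS: 12.80 × 0.13/(10.00 × √1.2) = 1.664/10.954 = 0.152; power at n = 67 is about 23%; 80% power needs about 343 completers.
- ITS: 1.57 × 0.40/(3.44 × √1.2) = 0.628/3.768 = 0.167; power at n = 67 is about 27%; 80% power needs about 285 completers.

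The gap comes from the spread. Poisson SDs would be √12.80 = 3.58 and √1.57 = 1.25, against 10.00 and 3.44 in Table 1.

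**5. Was Table 1's spread used elsewhere?** Yes, for log(TNE). With dz = (m2 − m1)/√(s1² + s2² − 2·0.4·s1·s2), Hi v Lo is:
- DS: (2.72 − 3.60)/√(1.28² + 1.62² − 0.8 × 1.28 × 1.62) = −0.88/1.614 = −0.545 (stated −0.55).
- ITS: (2.31 − 3.07)/√(0.80² + 1.29² − 0.8 × 0.80 × 1.29) = −0.76/1.216 = −0.625 (stated −0.63).

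Power exceeds 99% in both, as stated. The negative sign means TNE is lower on Lo than on Hi. On the raw scale Table 1 has 59.50 v 33.08 in DS and 28.37 v 15.88 in ITS. That is opposite to Aim 1.

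**The case against.** The best reply is that the plan sizes CPD by detectable effect. CPD appears in every row of Table 2, Hi against Lo has its own detectable ratio, and the 5% entry says nothing about the design because it would be 5% at any sample size. The plan also admits that no data existed for the Hi or Lo conditions and calls its values presumptive, so equal means can be read as placeholders.

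Much of this stands. A reader might infer from the 5% that the CPD half of Aim 1 is planned to fail, or that the study has no power for CPD. The documents do not support that: they claim 81% and 82% power at 1.13 and 1.40. Nor is it fair to call the statement linking the sample size to Aim 1 simply false, since CPD was considered. The x flag is also used loosely: Table 2 attaches it to DS rows with a ratio of 0.90 and 61.4% power.

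What does not stand is that this removes the conflict. The equal means are labelled anticipated, a detectable ratio is not an expected one, and no non-null Hi against Lo CPD ratio appears anywhere as the hypothesised effect.

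A second reply is that n = 67 understates the daily-smoker group. If 380 enrol, with 80 in the JUUL arm and 80 ITS, eGo daily smokers could number 380 − 160 = 220, or 220 × 0.85 = 187 after 15% attrition. Scaling the plan's own figure, exp(ln 1.13 × √(67/187)) gives a detectable ratio of about 1.08. That is fair, and it shows that the n needs stating. It does not help at a ratio of 1.00. With Table 1's SDs, power at 1.13 would be about Φ(0.152 × √187 − 1.96) = Φ(0.12), or 55%.

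**Conclusion.** The inconsistency is real and in the current text. Aim 1 predicts lower CPD on Hi; Tables 1 and 2 plan for equal CPD in both smoker groups, and the text says so for ITS. The point is a missing planning value and an ambiguous reading of the result, not an absence of CPD power at every effect size.

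The second part is a caution. The quoted detectable ratios appear to rest on near-Poisson variance. With Table 1's SDs, r = 0.4 and n = 67, power at those ratios is about 23% in DS and 27% in ITS, against the stated 81% and 82%. This assumes a two-sided 0.05 test without the planned False Discovery Rate correction, and uses a paired t-test as an approximation. The planned mixed or Poisson model could do better or worse, depending on how it handles overdispersion. The inconsistency itself does not depend on this calculation.

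**What to change.** Reconcile Aim 1, in both places where it is stated, with Tables 1 and 2 before analysis. Either:

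- **(a)** enter in both tables the Hi against Lo CPD ratio actually hypothesised, and state its power at a clearly given number of eGo daily smokers and of intermittent smokers, with a variance consistent with Table 1's SDs; or
- **(b)** keep equal CPD, drop the directional CPD hypothesis, report the Hi against Lo CPD ratio with its 95% CI and read a null result only against that interval, and amend the opening of the Power analysis to say that CPD was sized only by minimum detectable effect.

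Under (b), do not re-base the sample size on log(TNE) alone. Table 1 has TNE higher on Hi, so that edit would leave Aim 1 contradicting its own planning values unless the TNE direction is reconciled too.

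The cost is protocol wording and one re-run of the power table. No change to data collection or enrolment is required. Either the stated CPD power or the CPD claim becomes less favourable.

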**Aim 2 (Exploratory): To explore the effects of switching to VLNCCs plus ECIG-Hi or ECIG-Lo nicotine doses on abuse liability using biochemical measures of product use, compensation, and toxicant exposure, and self-reported measures of withdrawal, craving, affect, and satisfaction.** On an exploratory basis, we will examine the differences of ECIG dose (VLNC+ECIG-Lo vs. VLNC+ECIG-Hi) on additional measures of abuse liability, including ECIG puff count, withdrawal, craving, negative affect, minor tobacco alkaloid (MA) levels, acrolein DNA adduct levels, expired CO, RRE (i.e., purchase tasks), and liking (implicit attitudes, perceived harm, product satisfaction ratings).

**Aim 3 (exploratory): To explore the effects of switching from usual-brand cigarettes to VLNCCs, and from VLNCCs to VLNCC+ECIGs on measures of abuse liability.** On an exploratory basis, we will examine potential changes in the abuse liability measures from Aims 1 & 2 between the UB cigarette and VLNCC only phases, and between those phases and the dual-use phases (VLNC+ECIG-Lo and VLNC+ECIG-Hi).

**Aim 4 (exploratory): To characterize the effects of dual use of VLNCC and JUUL ECIGs on abuse liability.** On an exploratory basis, we will examine the differences in measures of abuse liability between the two phases of dual-use (VLNC+JUUL-Lo vs. VLNC+JUUL-Hi) among participants assigned to the JUUL ECIG arm.

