##### **Study overview**

Participants will be up to 380 (including up to 80 intermittent [ITS]) non-treatment-seeking adult smokers who are not regular e-cig users. Participants will smoke their usual brand (UB) during Phase 1 (Baseline; week 1) and will exclusively smoke the VLNCC during Phase 2 (weeks 2-4). During phases 3 (weeks 5-7) & 4 (weeks 8-10), smokers will be instructed to freely use any combination of assigned VLNCC and e-cigs (VLNCC+ECIG). All subjects will receive both e-cig doses (ECIG-Hi [36 mg/ml] and ECIG-Lo [8 mg/ml]) with order counter balanced across phases 3 and 4. At least 80 daily smokers will be randomized to the JUUL condition (VLNCC for phase 2 and combined VLNCC+JUUL-Hi or -Lo for phases 3 & 4). All participants in the JUUL group will receive both e-cig doses (JUUL-Hi [JUUL 5%; 59 mg/ml nicotine] and JUUL-Lo [JUUL 3%; 35 mg/ml nicotine]), with order counter-balanced across phases 3 and 4.

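### The power section contradicts itself on Aim 4 and claims adequate power with no JUUL effect stated; the 67 analysed ITS is not reconciled with 77% reported retention or with two ITS targets

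*Combined protocol and SAP*

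**What the plan says.** All statements are in the combined protocol and SAP.

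**Aim 4.** The Power analysis (section D, Statistical Approach & Expected Outcomes) makes three statements close together:

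- "Power estimates for the exploratory Aims 2, 3, and 4 analyses focuses on the GLMMs for self-report and volatility measures". The figure that follows is for r = 0.5 and alpha 0.05: "n = 67 DS participants provides 80% power for the GLMM to detect" a Cohen's f of 0.17.
- "The Aim 4 hypotheses are considered exploratory and were not subject to power analyses, but we should have adequate statistical power".
- The ground for adequacy is that Aim 4 should be able "to detect the hypothesized differences because it will use the same sample size, design, and outcome measures" as Aims 1 and 2.

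In section A, Aim 4 reads "we will examine the differences in measures of abuse liability between the two phases of dual-use (VLNC+JUUL-Lo vs. VLNC+JUUL-Hi"), with no direction or size. Its analysis paragraph in section D also covers "nicotine compensation (TNE, MA, expired CO"), alongside product use, liking and purchase-task indices. On size, the Study overview says "At least 80 daily smokers will be randomized to the JUUL condition".

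**ITS numbers.** The Study overview makes 80 a ceiling for ITS; the Power analysis makes 80 a floor. The Power analysis assumes 15% attrition, citing 92–100% completion across visits in the earlier U54 trial, and says "we based our power analysis on n = 67 DS and n = 67 ITS". Under Potential Problems & Alternative Strategies, the unplanned interim review of adverse events (176 smokers exposed) reports 77% retention to the end of this study.

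**The concern.** A reader cannot tell whether Aim 4 was powered. Power is adequate only relative to some effect, and the plan names none for JUUL. The wording would let a null JUUL Hi v Lo result be reported as an adequately powered null, in a study meant to inform FDA regulation.

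For ITS, whether the 67 behind Table 2 can be reached at the trial's reported retention depends on which enrolment wording holds. The power section keeps a loss rate taken from another trial and does not mention the figure from this one.

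**Working it through.** **1. Reproducing the plan's figures.** Expected ITS completers: 80 × 0.85 = 68, close to the stated 67.

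Table 2's log(TNE) effects follow from Table 1 with the stated correlation of 0.4:

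dz = (m₂ − m₁) / √(s₁² + s₂² − 2 × 0.4 × s₁ × s₂)

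- ITS, VLNC v ECIG-LO: (2.31 − 1.74) / √(1.49² + 1.29² − 0.8 × 1.49 × 1.29) = 0.57 / 1.532 = 0.372 (Table 2: 0.37).
- Hi v Lo, absolute values: DS 0.545 (Table 2: 0.55), ITS 0.625 (Table 2: 0.63).

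A paired t test (alpha 0.05, taken as two-sided) with n = 67 and dz = 0.372 has 85.1% power. The plan states 85.7% from 1000 simulations, whose standard error is √(0.857 × 0.143 / 1000) = 1.1 points. The two agree.

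**2. ITS at 77% retention.** The assumption is that the pooled interim figure applies to ITS.

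- Enrolment needed for 67 completers: 67 / 0.77 = 87.0, so 87–88.
- Completers from a cap of 80: 80 × 0.77 = 61.6, so 61–62.

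| Completers | ITS VLNC v LO log(TNE) power (dz 0.372) | dz detectable with 80% power |
|---|---|---|
| 67 | 85.1% | 0.347 |
| 62 | 82.2% | 0.362 |
| 61 | 81.6% | 0.365 |

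ITS-specific retention is not reported. Over an assumed 70–85%, 80 enrolled give 56–68 completers, power of 78–86%, and detectable dz from 0.381 down to 0.345.

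Hi v Lo log(TNE) power at 61 completers is 98.7% for DS and 99.8% for ITS, against 99.3% and 99.9% at 67.

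For ITS CPD only a rough scaling is possible: take the standard error implied by Table 2 and multiply it by √(67/61). The detectable risk ratio for Hi v Lo moves from 1.40 to about 1.42, and for VLNC v either e-cigarette phase from 0.73 to about 0.72. Power for the anticipated ratio of 0.64 goes from 98.7% to about 97.9%. These do not replace rerunning the plan's simulation.

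**3. What f = 0.17 means for Aim 4.** With m = 2 phases, the noncentrality is λ = n × m × f² / (1 − r) = 4nf² at r = 0.5. For a paired test λ = n × dz², so dz = 2f = 0.34. At n = 67 this has 78.3% power; 80% needs f = 0.174, a rounding difference. So the figure is a usable detectable effect, but the plan ties it to self-report and volatility measures, while Aim 4 also includes biomarkers.

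**4. Is adequacy supported?** The same n and design give the same detectable effect. They do not give the same true effect. From the Study overview, the eGo contrast is 36 v 8 mg/ml (ratio 4.5) and the JUUL contrast 59 v 35 mg/ml (ratio 1.69). The Procedures section gives 36 mg/ml for JUUL-Lo (ratio 1.64); the two sections need reconciling, but the comparison is the same either way. The eGo DS value of dz 0.55 therefore cannot simply be carried across. Power over an assumed range of JUUL effects:

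| Assumed dz | n = 67 | n = 61 |
|---|---|---|
| 0.20 | 36% | 34% |
| 0.30 | 68% | 64% |
| 0.35 | 81% | 77% |
| 0.55 | 99% | 99% |

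Adequacy thus needs dz of about 0.35 or more, a condition the plan neither states nor justifies.

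**The case against.** The defence has real force.

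- **The arithmetic is sound.** The 67, the dz values and the stated power all reproduce. This stands: the issue is an assumption that was not updated, plus conflicting wording.
- **The plan does supply a basis for Aim 4.** Table 2 gives DS Hi v Lo detectable effects at n = 67 (dz 0.35 for log(TNE), risk ratio 1.13 for CPD), and the JUUL arm has at least 80 daily smokers. This stands too. A reader might infer that Aim 4 has no power basis at all, or that it is underpowered. The documents support neither reading; what is missing is a justified JUUL effect.
- **The one log(TNE) power figure that visibly moves is not primary.** VLNC v VLNC+ECIG falls under exploratory Aim 3, and its power stays above 80%.
- **Completer counts overstate the loss.** The mixed models keep partial data. Because dose order is counterbalanced, participants given Lo in Phase 3 can supply both VLNC and Lo data without finishing Phase 4. So about 82% is a lower bound at the assumed retention.
- **The 77% is pooled and interim.** It is not split by DS/ITS or by device, so applying it to ITS or to the JUUL arm is an assumption.
- **Aim 4 is consistently labelled exploratory,** which limits the risk of misreading.

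These points reduce the severity. They do not remove the contradiction over Aim 4, the unsupported word on adequacy, or the conflict between a ceiling and a floor of 80.

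**Conclusion.** The point holds as a minor inconsistency in stated power.

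1. **Aim 4.** The text both gives and denies a power estimate, and its adequacy claim has no JUUL effect behind it. A detectable dz of about 0.35 at 67 completers is what the design supports.
2. **ITS.** The two targets agree only if exactly 80 enrol. Assuming the pooled 77% applies to ITS, 67 completers need 87–88 enrolled, which the floor permits and the ceiling does not. At the ceiling, 61–62 complete. The completer lower bound for ITS VLNC v ECIG-LO log(TNE) power is about 82% against the stated 85.7%, and detectable dz is about 0.36 against 0.35.

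A reader might infer that the primary comparison is endangered. For log(TNE) it is not: Hi v Lo power stays at about 99% or higher in both groups. For CPD, the rough scaling shows only small shifts, and the exact values need the plan's own simulation.

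**What to change.** - **ITS target.** Use one wording, ceiling or floor, in both the Study overview and the Power analysis.
- **Retention.** State the reported 77% beside the assumed 15%. Add the ITS log(TNE) power and detectable effect at 61–62 completers, labelled as a pooled interim assumption and as a lower bound because the mixed models use partial data. Rerun the existing simulation at that number for the ITS CPD columns of Table 2.
- **Aim 4.** Replace the adequacy claim with, for example: *Aim 4 is exploratory and no JUUL effect is assumed. With 67 completers the Hi v Lo contrast has 80% power for dz of about 0.35. If the pooled interim retention of 77% is assumed for the minimum 80 enrolled (about 61 completers), the figure is dz of about 0.36. Results are reported as estimates with confidence intervals.* Then either take Aim 4 off the list covered by f = 0.17 or delete the statement that it had no power analysis.

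The cost is wording, a few table figures and one simulation rerun, with no change to design, sample size or analysis. The stated figures become slightly less favourable and the Aim 4 adequacy claim is given up.
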